## Abstract

**Background:** Binge Drinking (BD), a pattern of alcohol misuse widely prevalent among youngsters, has been associated with altered inhibitory control and augmented reactivity to alcohol-related information. Memory inhibition (MI), the ability to voluntarily suppress unwanted thoughts or memories, has shown to lead to forgetting of memories in several psychiatric conditions. However, despite its potential clinical implications, no study to date has explored the MI abilities in populations with substance misuse, such as binge drinkers (BDs).

**Method:** This study protocol aims firstly to examine the behavioral and electroencephalographic (EEG) correlates of MI among college BDs. For this purpose, 45 BDs and 45 age-matched non/low-drinkers will be assessed by EEG while performing the Think/No-Think Alcohol task, a paradigm that evaluates alcohol-related MI. Additionally, this work aims to evaluate an alcohol-specific MI training protocol using cognitive and transcranial direct current stimulation (tDCS) while its effects on behavioral and EEG outcomes are assessed. For that, BDs will be randomly assigned to one of three training groups: *combined* (verum cognitive training [CT] and tDCS applied over the right dorsolateral prefrontal cortex [DLPFC]), *cognitive* (CT and sham tDCS), or *control* (sham CT and sham tDCS). Training will occur in three consecutive days, in three sessions. MI will be re-assessed in BDs through a post-training EEG assessment. Alcohol use and craving will be measured at the first EEG assessment, and both 10-days and 3-months post-training. In addition, behavioral and EEG data will be collected during the performance of an alcohol cue reactivity (ACR) task, which evaluates attentional bias towards alcoholic stimuli, before and after the MI training sessions.

**Discussion:** This protocol will provide the first behavioral and neurofunctional assessment of MI in BD. Along with poor MI abilities, BDs are expected to show alterations in the amplitude of several event-related potentials (ERPs) linked to MI (e.g., N2 and late parietal positivity) as well as abnormal functional connectivity (FC) patterns within/between regions associated with MI (e.g., DLPFC and hippocampal/parahippocampal regions). Results should also demonstrate the effectiveness of the training protocol, with BDs exhibiting an improved capacity to suppress alcohol-related memories after both *combined* and *cognitive* MI training, along with a significant reduction in alcohol use and craving in the short/medium-term. Furthermore, this protocol should also lead to significant modifications in the ERP and FC patterns, reflecting stronger MI capabilities and reduced alcohol cue reactivity in trained BD participants. Finally, in case the protocol provides significant results, these findings might have major implications for the understanding and treatment of alcohol misuse.

## Statistical Analysis

The first step of the statistical analyses will be to examine the behavioral and EEG correlates of MI among college BDs and non/low-drinkers. For that purpose, the outcomes of the TNTA task collected during the pre-training assessment (T2) in BDs and non/low-drinkers will be compared and correlated with alcohol consumption (AUDIT) and alcohol craving measures (i.e., the PACS' and ACQ-SF-R's scores, and the ERPs and valence/arousal ratings recorded during the ACR task). Secondly, with the purpose of verifying the impact of the *combined, cognitive* and *control* training procedures applied to BDs on psychological, behavioral and neurofunctional measures, the pre-training data (T2) from the 45 BDs will be compared with the post-training data (T4) from the same subjects. Thirdly, to examine potential differences in the psychological, behavioral and neurofunctional effects of the training sessions both in terms of MI abilities and alcohol craving/consumption, the results of the post-training assessment (T4) of the three training groups will be compared.

With regard to the behavioral data, items learned during the learning phase and correctly recalled during the memory test phase will be considered correct responses. Accordingly, the percentage of correct responses (for Think, No-Think and Baseline items) will be computed according to the following formula:

$$\left( \frac{\text{number of correctly recalled items}}{\text{number of previously learned items}} \right) \times 100$$

A mixed-model analysis of variance (ANOVA) with one between-subject factor, Group (non/low-drinkers, BDs), and two within-subject factors, Condition (Think, NoThink, Baseline) and Content (Alcohol, Non-Alcohol) will be conducted on the recall accuracy rate to examine the participants' MI ability at T2. Afterwards, a repeated-measures ANOVA with three within-factors: Moment (T2 and T4), Condition (Think, NoThink, Baseline) and Content (Alcohol, Non-Alcohol) will be performed to explore the training effects on the MI ability of BDs only.

Furthermore, in order to examine the emotional response of participants to alcoholic cues (self-assessed during the ACR task using the Manikin test) at T2, two ANOVAs with Group (non/low-drinkers, BDs) as between-subject factor and with Content (Alcoholic, Non-Alcoholic) as within-subject factor will be conducted for valence and arousal ratings, separately. In addition, to evaluate possible variations in valence and arousal responses as a function of training sessions, new ANOVAs will be performed for each training group with two within-factors - Moment (T2 and T4) and Content (Alcoholic, Non-Alcoholic).

For the TNTA task, we will analyse the ERPs, specifically the mean amplitudes of N2, LPP and frontal slow wave (FSW). A mixed-model ANOVA with one between-subject factor Group (non/low-drinkers, BDs) and four within-subject factors: Condition (Think, NoThink), Content (Alcohol, Non-Alcohol), Region (Left, Midline, Right) and Electrode (2 electrodes) will be conducted on the mean amplitude of each component to explore the MI neural mechanisms during pre-training (T2). A repeated-measures ANOVA with five within-subject factors: Moment (T2 and T4), Condition (Think, NoThink), Content (Alcohol, Non-Alcohol), Region (Left, Midline, Right) and Electrode (two electrodes) will be conducted on the mean amplitude of each component separately, to explore the effects of MI training on the neural activity.

For the ACR task at T2, the mean amplitude of the P1, N1 and P2 ERP components will be analysed by means of separate mixed-model ANOVAs with one between-subject factor Group (non/low-drinkers, BDs) and three within-subject factors: Content (Alcoholic, Non-Alcoholic), Region (Left, Midline, Right) and Electrode (two electrodes of interest). Furthermore, in order to investigate potential MI training effects on the electrophysiological reactivity to alcoholic cues, the amplitude of the abovementioned components will be analysed through repeated-measures ANOVAs using within-subject factors: Moment (T2 and T4), Content (Alcoholic, Non-Alcoholic),

Region (Left, Midline, Right) and Electrode (two electrodes). The behavioral and ERP correlates of MI and alcohol craving/reactivity will be correlated with the scores obtained from AUDIT, ACQ-SF-R and PACS.

In addition, analysis of the brain FC will also be conducted. FC will be calculated in the four classical bands –i.e., theta (4 – 8 Hz), alpha (8 – 12 Hz), beta (12 – 30 Hz), and low gamma (30 – 45 Hz)- using the Phase Locking Value (PLV) [70]. In a first step, PLV will be calculated separately for each pair of source positions, generating a 1489 x 1489 FC matrix. Secondly, we will average the PLV values of all the links connecting each pair of 58 cortical regions of interest (ROI) according to the Harvard-Oxford atlas, obtaining a 58 x 58 whole-brain FC matrix. For the whole-brain analysis, the PLV value between each pair of ROIs will be compared between groups by an ANCOVA test using Beamformer filter correlation (in order to correct potential source leakage differences between groups) as covariate and gender as factor. The resulting *p*-values will be corrected for multiple comparisons (number of pair comparisons and number of frequency bands) with a False Discovery Rate (FDR) of 0.1. Only links that survived the FDR-corrected threshold will be reported as significant. Once the significant links for each condition have been determined, the FC values will be correlated with the scores obtained from AUDIT, ACQ-SF-R and PACS.

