consumed per hour], number and type of drinks consumed in a standard week, percentage of times getting drunk when going out, age of onset of regular and BD) to assess participants' drinking patterns; 2) the DUDIT-E to examine the consumption of other drugs; 3) the Penn Alcohol Craving Scale (PACS) and the Alcohol Craving Questionnaire-Short Form Revised (ACQ-SF-R) to assess the alcohol craving; 4) the Barratt Impulsivity Scale-11 (BIS-11) and the short form of the Urgency-Premeditation-Perseverance-Sensation Seeking-Positive Urgency (UPPS-P) impulsive behavior scale to assess participants' impulsiveness; 5) the Symptom Checklist-90-Revised questionnaire (SCL-90-R) to evaluate the presence of psychopathological traits; 6) a clinical history interview to explore the personal/family history of psychopathological and neurological disorders as well as the overall medical history of the participants; and 7) the Edinburgh Handedness Inventory (EHI) to evaluate the participants' handedness.

T2: Pre-training EEG Assessment

During the pre-training EEG assessment, psychological (i.e., craving levels), behavioral (i.e., alcohol consumption levels and task performance) and neurofunctional (e.g., ERPs, brain FC) outcomes will be assessed. EEG data will be collected while participants perform the ACR and the TNTA task. Before the EEG recording, participants will be asked to perform a breathalyzer test to ensure that blood alcohol concentration value is 0.0% (Alcoscan ALC-1). Along with the AUDIT, and in order to determine alcohol consumption levels during the previous week and the previous three months, we will administer the Alcohol Timeline Followback (TLFB) and the Typical and Atypical Drinking Diary (TADD), respectively. After filling in the questionnaires, participants will perform the ACR task. Participants' resting brain activity will be recorded for three minutes during eyes-closed prior to the TNTA task. Finally, they will perform the TNTA

task. The total duration of the pre-training EEG assessment will be approximately two and a half hours.

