At T4, participants will perform the ACR and TNTA tasks under the same procedure to the one undertaken during the T2.

T5: Monitoring of alcohol consumption and alcohol craving.

Ten days after the post-training EEG assessment, the primary craving and alcohol consumption outcomes will be assessed. For this purpose, we will administer the PACS, the ACQ-SF-R and the AUDIT. Additionally, three months post-intervention, BDs will answer the same questionnaires and also the TADD aiming at assessing medium-term effects of the MI training in the alcohol craving and consumption levels.

Management and Ethics

Ethical requirements for human research will be followed in full accordance with the Code of Ethical Principles for Medical Research Involving Humans Subjects outlined in the Declaration of Helsinki (64th World Medical Association General Assembly, Brazil, 2013). The Ethics Committee for Social and Human Sciences of University of

Minho approved the present protocol in December 12, 2018 (approval reference: CE.CSH 078/2018). Prior to enrolling in the study, subjects will be informed about the aims, conditions and procedure of the study. Two copies of the informed consent forms will be provided, both of which will be signed by the researchers and participants. It is researchers' responsibility to guarantee the anonymity of the participants and the confidentiality of the data. The files containing data from the participants will be identified by the participant's code, not the name. The document containing the records of participants' personal information (e.g., names, contacts, code) will be stored in a different location from the data files and will only be accessible to authorized researchers. All files will be password protected and stored by the researchers in secure locations. Participants will be able to cease their participation in the study at any time without any consequences related to the relationship between the research team, the participant and the university. If participants want to terminate their enrollment in the study or ask for their data to be deleted later, researchers will promptly erase all data from files and eliminate documents using a paper shredder. There are no risks associated to the research protocol. College students will receive gift vouchers in order to compensate for their participation.

References

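### The SAP compares the arms on craving and consumption at T4, where no craving questionnaire or drinking measure is clearly scheduled

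*SAP*

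**What the plan says.** The SAP, Statistical Analysis, sets out three steps. In the second, "the pre-training data (T2) from the 45 BDs will be compared with the post-training data (T4) from the same subjects", covering psychological, behavioral and neurofunctional measures. In the third, for effects on memory inhibition and "alcohol craving/consumption, the results of the post-training assessment (T4) of the three training groups will be compared".

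The protocol describes the visits as follows.

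- **T2** assesses "psychological (i.e., craving levels), behavioral (i.e., alcohol consumption levels and task performance", plus EEG outcomes. Of the instruments, it names the AUDIT, and for the previous week and previous three months "we will administer the Alcohol Timeline Followback (TLFB) and the Typical and Atypical Drinking Diary (TADD), respectively". The questionnaires come before the ACR task. PACS and ACQ-SF-R are named at T1 and T5, but not at T2.
- **T4** is one sentence: "At T4, participants will perform the ACR and TNTA tasks under the same procedure to the one undertaken during the T2".
- **T5**: "Ten days after the post-training EEG assessment, the primary craving and alcohol consumption outcomes will be assessed". For this, "we will administer the PACS, the ACQ-SF-R and the AUDIT". At three months the same questionnaires are repeated and the TADD is added.

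The SAP Abstract agrees with T2 and T5: "Alcohol use and craving will be measured at the first EEG assessment, and both 10-days and 3-months post-training". Research question 4 (Protocol, Quality assurance and randomization) asks whether training lowers drinking and craving at the 10-day and 3-month follow-ups.

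**The concern.** The SAP's only stated between-arm comparison of craving and consumption is tied to T4. The visit schedule does not clearly collect the self-report data for it there, while the follow-ups that do collect them have no arm comparison in the Statistical Analysis section. PACS, ACQ-SF-R and AUDIT appear in that section only as correlates.

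Two things are at stake. First, an analyst would have to choose the data source or the time point after the data are in, for 45 randomised binge drinkers in three arms. Second, if staff did repeat the T2 drinking questionnaires at T4, the long-window instrument would describe mainly drinking from before the training. A null T4 contrast on it would say little about the training.

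**Working it through.** The plan states no figure to reproduce. The check has two parts.

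**1. Schedule against analysis**

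| Measure | T2 | T4 | 10 days | 3 months |
|---|---|---|---|---|
| ACR ERPs, valence/arousal ratings | yes | yes | no | no |
| TNTA recall and ERPs | yes | yes | no | no |
| PACS, ACQ-SF-R | craving assessed, scales not named | not named | yes | yes |
| AUDIT | yes | not named | yes | yes |
| TLFB (previous week) | yes | not named | no | no |
| TADD (previous three months) | yes | not named | no | yes |

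The third step needs the T4 column for craving and consumption. Only the ACR row clearly supplies part of it, because the SAP counts the ACR ERPs and ratings among its craving measures.

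**2. What a repeated T2 drinking questionnaire would measure at T4**

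Inputs: training lasts three days in a row (SAP Abstract). The look-backs are one week for the TLFB and three months for the TADD (Protocol, T2), taken as 7 and 90 days. The gap g from the last session to T4 is not stated, so I assume g = 1 to 7 days and also look beyond that.

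Take training as days 1 to 3, T4 as day 3 + g, and the window as the W days before T4. Days before the first session = W − (g + 2), not below 0. That is 88 − g for the TADD and 5 − g for the TLFB. If training days also count as untrained, the TLFB figure is 8 − g, for g from 1 to 8.

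As an illustration, suppose drinking is spread evenly and truly falls by 30% from the first session. The fall visible on the TADD is then 0.30 × (g + 2)/90.

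| g (days) | TADD pre-training | Visible fall on TADD | TLFB pre-training | TLFB, training days counted as untrained |
|---|---|---|---|---|
| 1 | 87/90 = 96.7% | 1.0% | 4/7 = 57.1% | 7/7 = 100% |
| 2 | 86/90 = 95.6% | 1.3% | 3/7 = 42.9% | 6/7 = 85.7% |
| 4 | 84/90 = 93.3% | 2.0% | 1/7 = 14.3% | 4/7 = 57.1% |
| 5 | 83/90 = 92.2% | 2.3% | 0% | 3/7 = 42.9% |
| 7 | 81/90 = 90.0% | 3.0% | 0% | 1/7 = 14.3% |

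The TADD result is not sensitive to the assumption: at g = 30 it is still 58/90 = 64.4%, and it drops below half only when 88 − g < 45, that is from g = 44. The TLFB result is sensitive: the window is mostly pre-training only at g = 1 on the strict count, or up to g = 4 on the wider one. The documents give no AUDIT look-back, so no share can be computed.

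**The same instrument at three months.** A 90-day TADD taken 90 days after the last session covers days 3 to 92: 0 pre-training days, 1 training day and 89 days after. Counted from T4 instead, all 90 days lie after training.

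**The case against.** The strongest reply is that the T4 comparison is not empty.

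- **Craving.** The SAP's craving measures include the ACR ERPs and ratings. These are collected at T4 and have planned T2–T4 ANOVAs. This stands: a reader might infer that T4 has no craving data at all, and the documents do not support that. Only the questionnaires are in doubt.
- **Behavioral measures.** The protocol's T2 list includes task performance, which is measured again at T4. So the second step is not empty for behavioral outcomes. This stands too.
- **Same procedure as T2.** T4 could be read as repeating the T2 questionnaires. It is therefore too strong to say that none of the 45 binge drinkers will have a PACS or ACQ-SF-R score at T4. But the phrase most naturally governs how the two tasks are run, the SAP Abstract omits T4 from its measurement times, and the T2 section itself names neither scale. The ambiguity remains and needs a decision.
- **Harm.** If no questionnaire is given at T4, there is no T4 questionnaire result to misreport, and the T5 data are untouched. This limits the harm. It does not supply the missing arm comparison at the time points of research question 4.

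Simply striking consumption from T4 would also remove the only between-arm consumption comparison in the Statistical Analysis section. That is right, so the deletion must be paired with a stated comparison at follow-up.

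**Conclusion.** The mismatch is real. The SAP ties the three-arm craving and consumption comparison to T4. The protocol's T4 entry names only two computer tasks, and both documents place these outcomes at T2, 10 days and 3 months. The clearly scheduled T4 craving data are the ACR ERPs and ratings; PACS, ACQ-SF-R and consumption depend on a generous reading of one phrase.

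On that reading, a T4 TADD would be 96.7% to 90.0% pre-training for an assumed gap of 1 to 7 days. A reader might extend this to every drinking questionnaire, but the documents do not support that: for the TLFB it turns on the unstated gap, and for the AUDIT no window is given. The 1.0% to 3.0% visible fall applies to the TADD alone and rests on the assumed 30% effect, even drinking over the window and the assumed gap.

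**What to change.** Reconcile the protocol's T2, T4 and T5 sections with the SAP Abstract and Statistical Analysis:

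1. Limit the T2–T4 comparison and the T4 arm comparison to TNTA and ACR outcomes, and remove consumption from both.
2. State a between-arm comparison of PACS, ACQ-SF-R and consumption at 10 days and at 3 months, adjusted for the T2 value. Use the 3-month TADD as the consumption measure whose window lies after training; a T2 TADD is already scheduled as its baseline. At 10 days the only named consumption measure is the AUDIT, so say what period it is taken to cover.
3. Name PACS and ACQ-SF-R at T2 as the craving baseline.
4. State which instruments, if any, are given at T4, and the gap from the last session to T4.

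A T4 contrast on the craving scales is optional. If it is wanted, list PACS and ACQ-SF-R at T4 as well, before the ACR task.

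The cost is a short edit to both documents and a few minutes of questionnaires at existing visits (T2 is planned at about two and a half hours). The T2 baseline and any T4 questionnaires must be settled before those visits, because a missed score cannot be recovered.

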criteria: a) use of illegal drugs except cannabis (as determined by the Drug Use Disorders Identification Test-Extended [DUDIT-E], [3]); b) alcohol abuse (i.e., AUDIT \geq 20); consumption of medical drugs with psychoactive effects (e.g., sedatives or anxiolytics) during the two weeks before the experiment; c) personal history of psychopathological disorders (according to DSM-V criteria); d) history of traumatic brain injury or neurological disorder; e) family history of alcoholism or diagnosis of other substance abuse; f) occurrence of one or more episodes of loss of consciousness for more than 20 minutes; g) non-corrected sensory deficits; h) Global Severity Index (GSI) $>$ 90 (Symptom Checklist-90-Revised questionnaire [SCL-90-R], [4]) or a score above 90 in at least two of the symptomatic dimensions.

Quality assurance and randomization

The protocol will be implemented by three skilled researchers with expertise in behavioral and EEG assessments and tDCS interventions. Researchers will not be aware of the results of the pre-training EEG assessment and will be blind to the randomization procedure that will follow. The randomization of the BD groups will be performed by an independent researcher using Microsoft Excel. BDs will receive one of the following interventions: 1) Combined training (verum CT and tDCS applied over the right dorsolateral prefrontal cortex); 2) Cognitive training (active CT and sham tDCS); or 3) Control (sham CT and sham tDCS). Based on this experimental procedure, it is expected that researchers will be able to answer the following research questions:

1. How does BD affect alcohol-related MI in young adults? Namely, are the behavioral and electrophysiological MI mechanisms - specifically those related to the suppression of alcohol-related memories - altered in BDs when compared to non/low-drinkers?

2. What is the effect of a MI training on behavioral TNTA task performance?

Specifically, will the BDs show a reduced recollection of no-think images - mainly for alcoholic no-think images – after training?

3. Are the electrophysiological correlates underlying MI mechanisms and alcohol cue reactivity changed by MI training?

4. Will the MI training reduce alcohol consumption and craving levels at 10-day and 3-month follow-ups?

Experimental tasks

Alcohol Cue Reactivity (ACR) task

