EEG data will be recorded using the ActiveTwo Biosemi System (Biosemi, Inc.) from 64 electrodes placed according the 10-10 system [12] and digitized at a 512 Hz rate. Vertical and horizontal electrooculogram activity will be recorded to control for eye movements and blinks. Two additional electrodes will be placed on the mastoids, bilaterally, to provide the signal offline reference. Electrode impedances will be kept below 20 kΩ and the EEG signal will be filtered on-line with a 0.01–100 Hz band pass filter.

T3: MI Training Sessions

After the pre-training EEG assessment (T2), BDs will be randomly assigned to one of the three training subgroups: *a) Combined training; b) Cognitive training; or c) Control*. The participants' allocation to the training group will be done by an independent researcher who will be responsible to program the tDCS parameters. Thus, both participants and research team will be blind to the randomization procedure.

During T3, subjects will perform the variation of the TNTA task corresponding to the group to which they will be assigned. After the first phase of the task (i.e., Learning Phase), neuromodulation (sham or active) will be performed using tDCS - a non-invasive, painless and safe brain stimulation method capable of modulating cortical excitability through a weak constant electric current induced from two surface electrodes placed on the scalp [13]. Twenty minutes of 2 mA direct current will be applied to the scalp using a saline-soaked pair of 35 cm² surface sponge electrodes, through an Eldith DC Stimulator Plus (Neuroconn, Germany). To stimulate the right DLPFC, the anodal electrode will be placed over F4 according to the 10-20 international system for EEG electrode placement.

The cathode electrode will be placed over the contralateral supraorbital area. During the active simulation, the current will fade in for 15 seconds, will be constant at 2 mA for 20 minutes, and then will fade out for 15 seconds. During the sham stimulation, the electric current will fade in during 15 seconds until reaching 2 mA, then will be constant at 2 mA for 15 seconds and will fade out for 15 seconds. This procedure makes both active and sham stimulation indistinguishable for the participants. Before and after the training sessions, participants will answer to a continuous Visual Analog Scale that allows checking for possible secondary effects of the electrical stimulation.

T4: Post-training EEG Assessment

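### The only stated comparison of the three randomised arms uses T4 results, and no stated model brings the T2 value into an arm contrast, so precision may be lost

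*SAP*

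**What the plan says.** The SAP's Statistical Analysis section sets out three steps. The second compares T2 with T4 within the 45 binge drinkers. The third is the explicit contrast of the randomised arms: "the results of the post-training assessment (T4) of the three training groups will be compared". Its stated scope is both memory inhibition and alcohol craving/consumption. It gives no test, factor list or covariate.

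The models that follow in the same section are:

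- **Recall, T2 to T4:** a repeated-measures ANOVA with within-subject factors only, which "will be performed to explore the training effects on the MI ability of BDs only". Training group is not a factor.
- **ERPs, T2 to T4 (TNTA and ACR tasks):** within-subject factors only, again without training group.
- **Valence and arousal:** "new ANOVAs will be performed for each training group with two within-factors". Each arm is analysed by itself.
- **Functional connectivity:** each link "will be compared between groups by an ANCOVA test using Beamformer filter correlation" as covariate, with gender as a factor. The section does not say which groups are meant.

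On timing, the Protocol (T3: MI Training Sessions) says: "After the pre-training EEG assessment (T2), BDs will be randomly assigned to one of the three training subgroups". Research question 4 asks: "Will the MI training reduce alcohol consumption and craving levels at 10-day and 3-month follow-ups". Under T5 the Protocol says: "Ten days after the post-training EEG assessment, the primary craving and alcohol consumption outcomes will be assessed".

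**The concern.** Every T2 measurement on a binge drinker is taken before allocation, so it is a legitimate covariate that is already in hand. In this plan T2 enters only pre-post comparisons that ignore training group or are run inside one arm. Training group is named as a contrast only at T4. The two are never combined, so whatever T2 could explain of the spread between participants at T4 stays in the error term of the arm comparison. With 45 people over three arms, there is little precision to spare.

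There is a linked problem of timing. The outcomes the Protocol calls primary at T5 are craving and consumption at 10 days. The SAP's arm comparison claims those outcomes but dates them T4. As written, research question 4 has no stated arm comparison at the visits it asks about.

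**Working it through.** **Inputs.** The 45 binge drinkers and three arms come from the SAP Abstract. The allocation ratio is not stated, so 15 per arm (45/3) with no dropout is assumed. The documents give no r, SD, alpha or effect size and no power figure to reproduce. I use r from 0 to 0.7, SD = 1 and two-sided 0.05.

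**Variance of a pairwise arm difference, ANCOVA relative to T4-only.** One three-arm model, one covariate, a linear relation and a common slope:

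ratio = (1 − r²) × [1 + 1/(N − g − 2)], with N = 45 and g = 3, so ratio = (1 − r²) × (1 + 1/40) = 1.025 × (1 − r²).

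Break-even: 1 − r² = 40/41, so r = √(1/41) = 0.156, or 0.161 once the lost degree of freedom in the t critical value is counted.

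**Half-width of the 95% CI.** T4-only: t(42) × √(2/15) = 0.737 SD. Adjusted: t(41) × √(2/15) × √ratio. Equivalent unadjusted size per arm = 15/ratio. Power is for a true difference of 0.8 SD with pooled error.

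| Analysis | Variance ratio | Half-width (SD) | Equivalent n per arm | Power |
|---|---|---|---|---|
| T4-only | 1 | 0.737 | 15 | 57% |
| ANCOVA, r = 0 | 1.025 | 0.747 | 14.6 | 56% |
| ANCOVA, r = 0.3 | 0.933 | 0.712 | 16.1 | 60% |
| ANCOVA, r = 0.5 | 0.769 | 0.647 | 19.5 | 68% |
| ANCOVA, r = 0.7 | 0.523 | 0.533 | 28.7 | 84% |

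Simulation with 200,000 trials per value of r gave ratios of 1.026, 0.933, 0.771 and 0.523 at r = 0, 0.3, 0.5 and 0.7.

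**Dropout to 12 per arm (N = 36).** The factor is 1 + 1/31 = 1.032 and break-even is √(1/32) = 0.177. Simulated power is 48% for T4-only, against 50%, 58% and 75% at r = 0.3, 0.5 and 0.7.

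**Recall difference score (alcohol Baseline minus No-Think).** The Protocol (TNT Phase) gives 12 items per condition. An even split gives 6 alcohol items per cell, which is an assumption. Binomial noise in the difference has variance 2p(1 − p)/m. The largest possible r is then true variance/(true variance + noise). Assuming recall p of 60% or 80% and a true between-person SD of 10 or 20 points, with m = 6:

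- p = 0.6, SD 10: 0.01/(0.01 + 0.08) = 0.111, ratio 1.012
- p = 0.8, SD 10: 0.01/(0.01 + 0.0533) = 0.158, ratio about 1.000
- p = 0.6, SD 20: 0.04/(0.04 + 0.08) = 0.333, ratio 0.911
- p = 0.8, SD 20: 0.04/(0.04 + 0.0533) = 0.429, ratio 0.837

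The denominator is learned items, which may be fewer. With m = 5 the range is 1.016 to 0.873; with m = 4 it is 1.019 to 0.911.

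**Change scores.** Adding training group to the T2-T4 ANOVA and testing Group × Moment amounts to comparing change scores. Relative to T4-only its variance is 2(1 − r) with equal SDs: 1.4 at r = 0.3, 1.0 at 0.5 and 0.6 at 0.7. It beats T4-only only above r = 0.5, so it does not replace ANCOVA.

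**Timing, side by side.** The SAP's third step puts craving and consumption at T4. The SAP Abstract measures them at the first EEG assessment, 10 days and 3 months. The Protocol's T4 section names only the ACR and TNTA tasks. Its T5 section names PACS, ACQ-SF-R and AUDIT at both follow-ups and adds TADD at 3 months. No arm comparison is stated for 10 days or 3 months.

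**The case against.** The strongest reply is that the third step is an overview sentence. It names no model, so it neither adopts nor rules out a covariate, and a reader who infers that the SAP has chosen an unadjusted analysis goes further than the text. That stands. What can be said is that no stated model uses T2 in an arm contrast.

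The second reply is that the large gains may not materialise. The 48% reduction needs r = 0.7, and no document supports that value. For recall, the SAP's behavioural measure of memory inhibition, two of the four cases with 6 items per cell show no gain. ERP and rating contrasts are also difference scores and may have low r. The questionnaire totals, which escape that limit, are not named at T4. This stands too, and it limits the claim about size. It does not reverse the balance, because the worst case is 2.5% more variance.

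A reader might also infer that the SAP has no arm comparison for craving and consumption at all. It does not support that: the third step includes them, at T4. The defect is a mismatch between T4 and T5, which leaves the follow-up visits uncovered.

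Finally, reducing every outcome to one score would discard the regional and condition structure the SAP wants to examine. That is fair, and the fix does not require it.

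**Conclusion.** The point holds as one of precision and specification. The plan's only explicit arm comparison uses T4 results, and the pre-randomisation value of the outcome enters no stated arm contrast. If the functional connectivity groups include the arms, that ANCOVA still omits the T2 value.

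A reader might conclude that the T4 contrast is biased or its test invalid. It is neither, because randomisation protects both.

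The size of the loss is unknown because r is not given. Near r = 0.16 it is nil, at 0.3 it is modest, and it becomes material at about 0.5. These figures rest on all 45 being analysed in one three-arm model with one covariate, a linear relation and a common slope. The half-widths and power also rest on 15 per arm.

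Separately, the T4 label on craving and consumption conflicts with the visits at which the documents place those measures, and research question 4 has no stated arm comparison at 10 days or 3 months. This conclusion covers the SAP's Abstract and Statistical Analysis sections, the SAP text available. It merits a change to the SAP, but it does not threaten the trial's validity.

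**What to change.** - **Arm comparison at T4.** For the contrast that carries each hypothesis (for example alcohol Baseline-minus-No-Think recall), fit an ANCOVA of the T4 value on Training Group (three levels) with the same measure at T2 as covariate. Report the adjusted combined-control, cognitive-control and combined-cognitive differences with 95% CIs. The factorial ANOVAs over Condition, Content, Region and Electrode may stay alongside. State that little gain is expected for recall.
- **Functional connectivity.** Say which groups are compared. If they include the arms, add the T2 value of the same link as covariate.
- **Follow-up.** Reconcile the T4 and T5 timing of craving and consumption. Apply the same ANCOVA to PACS, ACQ-SF-R and AUDIT at 10 days and 3 months, and to TADD at 3 months. Name the covariate: the T2 value, with T1 used only where no T2 value exists. The Protocol's T2 section supports this for consumption: AUDIT is given there, and "we will administer the Alcohol Timeline Followback (TLFB) and the Typical and Atypical Drinking Diary (TADD), respectively". For craving it says levels are assessed at T2 but does not name the scales, so the SAP should.

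**Cost.** SAP wording and a stated contrast per hypothesis, with no new participants or data. Statistically, it costs one degree of freedom and at most about 2.5% more variance if r is 0 (3.2% at 12 per arm), which is about 1% in CI width at 15 per arm.
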